3.0 STUDY SCHEMA

4.0 INTRODUCTION

4.1 Background and Rationale

Although prison and jail can be effective at reducing levels of crime and drug use during the period of incarceration, resumption of these behaviors upon release is the norm. Nearly 7 in 10 released offenders are re-arrested within three years (Bureau of Justice Statistics, 2002; Pew Center on the States, 2011). Data regarding drug use are even more disquieting, indicating that in many cases offenders are re-addicted within one month of release from incarceration (Bird & Hutchinson, 2003; Kinlock et al., 2011) and their drug use and/or crime levels following prison can even exceed use levels prior to incarceration (Hough, 2002).

Not surprisingly, such persistent patterns of drug use and crime are associated with comorbid health problems and even premature death. In a given year, a quarter of all people in the United States who have HIV, a third who have HCV infection, and more than 40% who have tuberculosis disease will pass through a correctional facility that same year (Bergier et al., 2010; Hammett et al., 2002). Likewise, the risk of death among parolees during the first two weeks following release from prison is nearly 13 times greater than those of similar demographic background—with drug overdose being the leading cause (Binswanger et al., 2007). As dire as this finding is, it may be an underestimate of the problem. A study of newly released prisoners in England and Wales found that mortality rates among males were 29 times higher than the general population during the first two weeks of release. Female offenders' mortality rates were 69 times higher (Farrell & Marsden, 2007). These studies are included in a recent meta-analysis of drug-related deaths following prison release that revealed a three- to eight-fold increase in the risk of drug-related deaths during the first two weeks following release (relative to the subsequent 10 weeks), with relatively high risk of death remaining throughout the first month of reentry (Merrall et al., 2010). These authors concluded that "further research is urgently needed on mortality after release from prison, as well as interventions to reduce the risk of drug-related deaths during the transition from prison to the community" (pp. 1552-1553).

A substantial body of research now exists supporting the safety and efficacy of naltrexone and buprenorphine, in both their oral, daily-dose forms and in depot long-acting formulations (e.g., Chiang et al. 2003; Krupitsky et al., 2011; Ling & Wesson, 2003; Ling et al., 2010; Lobmaier et al., 2010; Mattick et al., 2008; Mello & Mendelson, 1980). Nonetheless, MAT, particularly pharmacotherapies other than methadone, has not been readily adopted in correctional settings. A survey of correctional agencies (conducted as part of NIDA's CJ-DATS collaborative) revealed that two-thirds of the jails surveyed provided methadone (primarily for detoxification), but *none* offered naltrexone to opiate-dependent inmates (Friedmann et al., 2012). Although the use of MAT is more common in jails than in prisons (used primarily to manage opiate withdrawal), it is important to note that MAT remains unavailable in most jails for purposes beyond detoxification (Oser et al., 2009).

The efficacy of naltrexone has been well established. Naltrexone, an opioid receptor antagonist, blocks the euphoric effects of heroin and other opioids. This characteristic has fostered growing acceptance of naltrexone by correctional authorities who wish to avoid the perception that they are merely replacing one drug with another (Farabee, 2006). However, it must be taken orally on a daily basis, making adherence a problem among all but the most committed patients. Cornish et al. (1997) randomly assigned federal probationers to a 6-month program of probation plus naltrexone and brief drug counseling or to probation plus counseling alone and found that opioid use was significantly lower in the naltrexone group, with the mean percent of opioid positive urine

tests among the naltrexone subjects at 8%, versus 30% for control subjects (p < .05). Likewise 56% of the controls and 26% of the naltrexone group (p < .05) had their probation status revoked within the 6-month study period and were returned to prison. But treatment compliance was a problem, with only 52% of subjects in the naltrexone group continuing for the 6-months duration of the study.

Still, the effectiveness of oral naltrexone is mitigated by poor compliance hampering clinical utility in real-world settings. In one study of a prison-based naltrexone program, only 7% of the enrolled patients remained in treatment for six months (Shearer, Wodak, & Dolan, 2007). To address this issue, Vivitrol[®] (~380mg naltrexone delivered intramuscularly every four weeks; Alkermes, Inc.) was developed to provide long-acting pharmacotherapy for one month per dose. The purpose of this proposed study is to assess the relative effects and net economic benefits of this pharmacotherapy in comparison with a patient navigator (PN) and drug education (DE) conditions for criminal-justice-involved offenders.

4.1.1 Issues of MAT in Correctional Settings

Although many have called for expanding the use of medication-assisted treatment in prison (Cropsey et al., 2005; Kinlock et al., 2011), there are several features of jails that make the latter more promising settings for MAT. Perhaps the most critical difference is that detoxification typically occurs in jails, not prisons. Virtually all prison inmates spend time in local jails while awaiting trial or sentencing. Therefore, whether an offender is serving a brief jail sentence or is awaiting transfer to prison, detoxification typically falls under the purview of the jails. The second reason for focusing on jails relates to the time period of incarceration. Jails tend to house offenders for a few days to several months, whereas prisons are reserved for those serving sentences for a year or more-on average 29 months (Kuziemko, 2007). As a result, the costs of maintaining prison inmates on naltrexone, buprenorphine, or methadone for the entire duration of their sentence would likely be prohibitive. The third consideration is that more offenders pass through jails than prisons. This is an important point that is often missed: Although prisons house more inmates than jails at any one time (1,512,576 in prison versus 780,581 in jail at year-end 2007 [BJS, 2008a]), the number of *entrants* to these two systems tells a very different story, with 751,593 admissions to prison during 2007 versus approximately 13 million admissions to jails during that same period (BJS, 2008a,b). The increased flow between jails and the community likely accounts for reports that the availability of drugs in jails exceeds that in prisons.

A recent survey of criminal justice agencies affiliated with NIDA's Criminal Justice Drug Abuse Treatment Studies (CJ-DATS) collaborative found that MAT is underutilized in the treatment of substance use disorders (Friedmann et al., 2012). Offenders most likely to receive MAT were pregnant women and those experiencing withdrawal. Offenders *least* likely to receive MAT were those re-entering the community after serving a prison or jail term. Among the primary factors influencing the use of MAT in these correctional settings were preferences for drug-free treatment and limited knowledge of the benefits of MAT. Addressing these philosophical- and knowledgerelated barriers requires relevant research, specifically, data collected in real-world settings testing practical MAT administration models on offender populations. It is also important to note that even if philosophical barriers shift in favor of MAT, tight local and state budgets may require a higher threshold of evidence—particularly related to costs—before allowing a wider adoption of MAT for offenders.

4.1.2 Preventing relapse to opioid addiction and reducing HIV transmission

Research has shown that substitution or maintenance medication is an effective way of managing opioid dependence, preventing relapse to drug use, and concomitantly resulting in reduced HIV/AIDS infection by curtailing drug-related behaviors that promote transmission of HIV (Metzger, Woody, & O'Brien, 2010; Morris, Levine, & Weaver, 2004; WHO, 2004). This aspect is especially pertinent among the criminal justice population, where the prevalence of confirmed AIDS is more than double that of the general U.S. population (Maruschack, 2009). Effective MAT also provides an opportunity to educate about unsafe sexual activities and to reduce HIV-risky sexual activities such as having concurrent/multiple sexual partners, especially in overlapping networks that greatly increase HIV infection liability (Copenhaver et al., 2006; Morris, 1997; Morris & Kretzschmar, 1997). Research has documented significant reductions in HIV risk behavior and overdose deaths and improved outcomes from antiretroviral treatment in HIV-infected opioid users when treated with buprenorphine (Johnson et al., 2000).

Naltrexone offers an approach to combat the spread of HIV predicated on its opioid antagonist mechanism of action, in contrast to the full or partial agonists (methadone or buprenorphine). Vivitrol may be especially useful where cultural and regulatory conditions inhibit use of opioid agonists with reinforcing aspects, because of perceived "coddling" of addicts. As promising as this long-acting pharmacotherapy may be, however it is unlikely to be widely adopted by correctional agencies or community treatment systems until their expected net economic benefits are established.

4.2 Significance of the Project to the Field

The efficacy of naltrexone has been well established in numerous controlled clinical trials conducted in community settings, however little research is available examining its impact among correctional populations. A recent study compared depot naltrexone with methadone among heroin-dependent inmates released from prison and found that both pharmacotherapies were associated with reductions in opiate use and criminal activity (Lobmaier et al., 2010). However, post-release retention in the methadone condition was extremely low (relative to the 100% adherence rate for those in the depot naltrexone group). Poor attendance/adherence is a vexing issue in offender treatment, with typical rates of admission of one-third to one-half of parolees referred to drug-free counseling programs, and about half of those referred to MAT (Cornish et al., 1997; Lobmaier et al., 2010; Olson, Rozan, & Powers, 2009). Vivitrol potentially obviates the problem of non-compliance with medication dosing, eliminates concerns about potential diversion as medication is provided once monthly by the medical study team, and lessens the need for frequent patient presentation in the clinic or primary care physician's office—issues that are concerns associated with oral naltrexone.

The development of long-acting depot formulations of naltrexone (e.g., Vivitrol) has also provided a new approach for treating opioid addiction, especially in terms of preventing relapse once abstinence has been attained (Comer et al., 2006). Naltrexone implants reliably prevented relapse within one month after detoxification (Foster, Brewer, Steele, 2003), and multi-site research in Russia found Vivitrol effective for treating heroin addiction over six months (Krupitsky et al., 2011). Vivitrol was approved in 2010 by the U.S. FDA for opioid addiction.

The pharmacotherapy examined in this study offers important advantages to its orally administered counterparts, including the eradication of concerns regarding medication

compliance, maintenance of consistent plasma levels of medication, and elimination of potential diversion and misuse. The proposed project intends to provide new empirical data from a correctional population on the utility of depot naltrexone in preventing relapse and associated behaviors by examining the long-acting medication in a context that takes advantage of its strengths to bring about positive and meaningful net economic benefits. Comparisons will be made between two medication conditions provided with and without a Patient Navigator component (VI, PNV) and a drug education (DE) condition.

4.3 Objectives

The project emphasizes evaluation of the clinical utility of pharmacotherapy with Vivitrol (VI) or Vivitrol + PN (PNV) in comparison to a drug education (DE) condition. Descriptive statistics will provide an overall assessment of the implementation of the protocol. The aims of this project include:

Aim 1: Assess the feasibility and clinical utility of a 24-week protocol of long-acting naltrexone (by intramuscular *injection*; VI) provided with and without a PN component (VI, PNV). Measures include side effects, adverse events, retention, and acceptance of the procedures by participants and clinicians. Acceptance will also be assessed among correctional staff.

Aim 2: Examine the effectiveness of Vivitrol provided with and without a PN component (VI, PNV) for its ability to prevent relapse to illicit opioid use, reduce drug-related criminal activity, curtail engagement in HIV-risk behaviors, and increase employment compared to a group receiving only drug education (DE) to assist in relapse prevention after release from jail. The VI and PNV groups will receive VI monthly for the entire 6-month intervention phase. Th PNV group will be provided with PN for 3 months to provide assistance in accessing community treatment after release from jail. Primary measures include DSM-5 diagnosis at time to relapse (defined as self-report of daily opioid use for one week), protocol adherence, and opioid-negative urine samples during the study.

Aim 3: Collect cost data using the Drug Abuse Treatment Cost Analysis Program (DATCAP) and estimate savings from reduced drug use, reduced criminal activity and re-incarceration, and increased employment. Data will support benefit-cost and cost-effectiveness analyses of depot pharmacotherapy with Vivitrol for released offenders with opioid use disorders.

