2.4 Analyses

The primary outcomes include opioid use and DSM-5 diagnosis of opioid use disorder via modified CIDI-2 Substance Abuse Module at 6-months post-intervention. Opioid use will be computed from the Timeline Follow-Back (TLFB) as the number of days of self-reported opioid use in the past 30 days at the 6-month assessment. The cost analysis will measure and value resources associated with VI, including medical personnel (physician/nurses), labs, and medications. To ascertain cost-effectiveness ratios of VI and PNV, cost data will be compared to changes in key clinical measures of effectiveness.

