4.3.1 Primary Objectives

The primary objective is to compare outcomes of the three intervention groups, measured a The opioid use and DSM-5 diagnosis of opioid use disorder via modified CIDI-2 Substance Abuse Module at 6-months post-intervention.

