6.1 Primary Outcome Measure

The primary outcomes will be opioid use and a DSM-5 diagnosis of opioid use disorder 6 months after randomization.

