6.2 Secondary Outcome Measures

- HIV risk behaviors (compared using repeated measures procedures to evaluate possible change in sexual and drug-related behaviors that may inhibit or promote HIV infection) measured by the HIV-GAIN;
- (2) Self-reported number of days incarcerated during the intervention and follow-up phases;
- (3) Self-reported number of days of opioid and other drug use measured by TLFB, and objective measures of drug use by urine drug screens (UDS) at the 6-month post-release assessment (end of the intervention phase);
- (4) Self-reported days in drug abuse treatment;
- (5) Self-reported number of arrests;
- (6) Self-reported craving for opioids;
- (7) Self-reported number of overdoses; and
- (8) Self-reported motivation for treatment.

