10.1 Primary Outcome

The primary outcomes of opioid use and a DSM-5 diagnosis of opiate use disorder 6 months after randomization.

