10.3 Power and Sample Size

With the primary focus of this study on the feasibility and clinical utility of the two pharmacotherapies, the study is not powered to be an exhaustive comparison but to parsimoniously enable preliminary characterization of outcomes that will be needed to inform a future, larger scale multi-site trial. We expect that a baseline sample of 150 participants with 50 participants per condition will yield a final aggregate sample of approximately 120 participants. assuming 10-20% dropout. (Our similar studies have had 85-90% follow-up rates.) Thus, a final evaluable sample size of 120 participants would permit detection of a medium-large effect size (~.60) between conditions for some of the outcome variables (at ~.70 power) and .5 effect size (at .80 power) for others. For example, we expect that the measure "time to first opioid use" will be markedly different among the three groups, given the difference given the expected relapse among the no-medication group. Over time, the total number of opioid-free urine results is expected be greater among the VI participants, who are likely to show less dropout and better long-term retention compared to the DE group. Our selection of the effect size is based on effects found in the literature for Vivitrol when compared against placebo, and is consistent with both Cohen (1988) and with more recent guidance; for example, Lipsey and Wilson (1993) did a meta analysis of 302 meta-analyses that included over 10,000 studies and found that the average effect size was .5, adding support to Cohen's recommendation that selection of the effect size of .5 is appropriate (Bausell & Li, 2002).

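### Aim 2's primary measures conflict with the primary pair in sections 4.3.1, 6.1 and 10.1 and the single primary in 10.0, and no alpha rule covers the pair

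*Combined protocol and SAP*

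**What the plan says.** Section 4.3, Aim 2, labels as primary: "Primary measures include DSM-5 diagnosis at time to relapse (defined as self-report of daily opioid use for one week), protocol adherence", followed by "opioid-negative urine samples during the study".

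Section 6.1 reads: "The primary outcomes will be opioid use and a DSM-5 diagnosis of opioid use disorder 6 months after randomization". Section 10.1 repeats the pair. Section 4.3.1 also has it, but times the diagnosis differently: "DSM-5 diagnosis of opioid use disorder via modified CIDI-2 Substance Abuse Module at 6-months post-intervention". The abstract (2.4 Analyses) gives the pair too, and is the only place that defines the opioid-use primary: "number of days of self-reported opioid use in the past 30 days at the 6-month assessment".

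Section 10.0 refers to one primary outcome measure, diagnosis at six months, and gives a dropout rule for it. Section 8.2.4 also treats the 6-month diagnosis as the primary outcome. The heading of 10.4.2 limits its model to the first primary outcome. No section gives a primary analysis for a second one.

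Secondary item (3) in 6.2, repeated in 4.3.2 and 10.2, is "Self-reported number of days of opioid and other drug use measured by TLFB", together with urine screens at the 6-month post-release assessment. Time to relapse and adherence are on neither list in section 6. The example in 10.3 is time to first opioid use, which the plan expects "will be markedly different among the three groups"; it is not a listed outcome either.

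**The concern.** If two parts of a plan name different primary outcomes, and neither yields to the other, the result that counts as success is not fully settled before the data are seen. Three features make that matter here.

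- The trial is open-label (7.14), and opioid use and relapse are self-reported.
- The Aim 2 measures have uses elsewhere in the plan. Section 10.4 plans a Treatment Effectiveness Score analysis of urine results, and 10.4.3 uses time to relapse as a cost-effectiveness measure. Either could be reported as primary by citing Aim 2.
- Section 10.0 tests everything at two-sided .05 unless stated otherwise, and nothing says whether one or both primaries must succeed.

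**Working it through.** **1. Primaries by section.**

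| Section | Called primary | Time point |
|---|---|---|
| 2.4 Analyses | opioid use; diagnosis | 6 months post-intervention; opioid days at the 6-month assessment |
| 4.3 Aim 2 | diagnosis tied to time to relapse; adherence; opioid-negative urines | relapse; during the study |
| 4.3.1 | opioid use; diagnosis | 6 months post-intervention |
| 6.1 and 10.1 | opioid use; diagnosis | 6 months after randomization |
| 10.0 | diagnosis | six months |
| 10.4.2 | diagnosis (first primary only) | six months post treatment (model); 6 months (contrast) |

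The count is one in 10.0, two in the pair, and three in Aim 2. Aim 2 gives four if its garbled first phrase is split into diagnosis and time to relapse. The relapse definition that follows supports the split, but it is an inference. Pooling Aim 2 with 6.1 then gives at most five: diagnosis, opioid-use days, time to relapse, adherence and urines.

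**2. Time anchor.** The intervention lasts 24 weeks. Read literally, six months (about 26 weeks) after its end is 24 + 26 = 50 weeks, near the month-12 visit. Six months after randomization is near the month-6 visit.

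**3. Overlap of roles.** The abstract's primary is TLFB opioid days in the past 30 at the 6-month assessment. Secondary item (3) uses the same instrument and quantity and, on the natural reading, the same visit. It does not restate the 30-day window, so identity is probable rather than explicit. Urine results are primary in Aim 2 over the whole study and secondary at month 6 in 6.2.

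**4. Error rate.** The plan gives only the per-test .05, so there is no overall rate to reproduce. For k independent tests, P(at least one false positive) = 1 − 0.95^k:

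- k = 1: 5%
- k = 2: 1 − 0.9025 = 9.75%
- k = 4: 1 − 0.8145 = 18.5%
- k = 5: 1 − 0.7738 = 22.6%

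These outcomes track related behaviour and are probably positively correlated. The documents give no correlations, so two were assumed and simulated (one million draws of equicorrelated normal statistics, two-sided 1.96):

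| k | correlation 0 (formula) | 0.5 | 0.9 |
|---|---|---|---|
| 2 | 9.75% | 9.0% | 7.0% |
| 4 | 18.5% | 15.6% | 9.3% |
| 5 | 22.6% | 18.3% | 10.1% |

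**5. Power statement.** Section 10.3 gives an effect of about .60 at about .70 power for some outcomes and .5 at .80 for others, without tying either to an outcome. With 120/3 = 40 per arm, two-sided .05, power = Φ(d√(n/2) − 1.960):

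- d = 0.60: Φ(2.683 − 1.960) = 0.765
- d = 0.5: Φ(2.236 − 1.960) = 0.609

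Neither stated pair reproduces. That is a separate matter, and nothing here rests on it.

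**The case against.** The best reply is that Aim 2 stands alone. Four sections name the same pair, 10.0 and 8.2.4 point to diagnosis, and 10.4.2 fixes a model and contrast for it. One loosely worded sentence in an aims narrative, whose first item is itself the diagnosis, hardly outweighs them. This stands as a limit on the room for choice. It does not close it. The four sections disagree on timing, opioid use has no primary analysis and sits on both lists, and no text makes Aim 2 subordinate.

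A reader might infer that the plan lists five rival primaries and so carries a 22.6% error rate. The documents do not support that. No section lists five; reaching five takes pooling two sections and splitting a garbled phrase. The 22.6% is the independence bound. Adherence is also a doubtful between-arm test, since the DE arm receives no medication and no such test is specified.

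Two further replies have some weight. Section 10.3 describes the trial as a preliminary characterization, which lessens the force of a confirmatory error argument; but a trial meant to inform a larger one still needs one agreed primary. And time to first opioid use is offered only as an example. That is true, but no listed primary is powered in its place.

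**Conclusion.** The plan is wrong as written. Aim 2 conflicts with 2.4, 4.3.1, 6.1 and 10.1, and all of these conflict with the single primary in 10.0. The consequence is bounded. For the pair that most of the plan supports, the chance of at least one false positive is up to 9.75% without an alpha rule, and 7.0% at an assumed correlation of 0.9. If every measure called primary anywhere were open to selection, it would be about 10% to 22.6% for assumed correlations from 0.9 down to 0. That range is an illustration of the exposure, because it depends on the assumed correlations and on counting five measures. It should not be read as the trial's actual error rate, nor the primary as wholly open to choice.

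**What to change.** 1. Make Aim 2 and 10.0 match 6.1 and 10.1: diagnosis and opioid-use days as the only primaries, with the abstract's definition of opioid-use days carried into 6.1.
2. Add time to relapse, adherence and opioid-negative urines during the study to the secondary list.
3. In secondary item (3), in 4.3.2, 6.2 and 10.2, remove only the opioid-days part. Keep other drug use and urine screens.
4. State one time anchor and the visit it maps to, and use it in 2.4, 4.3.1, 6.1, 10.0, 10.1 and 10.4.2.
5. Specify an analysis for opioid-use days and one alpha rule for the pair. One option is to test diagnosis first at two-sided .05, in line with 10.4.2's ordering, and opioid-use days only if diagnosis succeeds.
6. Tie the power statement to a listed primary.

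The cost is a wording amendment, which 11.2 requires the IRBs to approve before it takes effect; no new data are collected. The Aim 2 measures lose primary status. Fixed order costs diagnosis no power, but opioid-use days cannot be claimed if diagnosis fails. Splitting alpha to .025 each would, for a continuous outcome with 40 per arm and an effect of 0.60, lower power from 0.765 to Φ(2.683 − 2.241) = 0.671.
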